8.1.1.6 Body surface area (BSA)-Psoriasis

The BSA palm method will be used for the evaluation of BSA affected by psoriasis as follows:

The subject's hand, including the palm, fingers and thumb, is used as the reference point for measuring how much of their skin is affected by psoriasis, representing roughly 1% of the body's surface.

- Subject's palm=1%
- Head and neck=10% (10 palms)
- Upper extremities=20 % (20 palms)
- Trunk=30% (30 palms)
- Lower extremities=40 % (40 palms)

Total BSA=100%.

8.1.2 Primary analysis of the primary efficacy variable

The primary efficacy variable (ACR50 at Week 12) will be analyzed for all subjects in the FAS.

The dose-response relationship between treatment and ACR50 response will be assessed with an ordered categorical analysis using a nonparametric correlation statistic of Mantel and Haenszel

(Mantel and Haenszel, 1959) and modified ridit scores (Bross, 1958) with the corresponding p-value.

The analysis will include geographic region and prior TNF inhibitor exposure as stratification factors. Prior TNF inhibitor exposure will be used as a stratification factor as it may have an impact on efficacy. The use of geographic region as a stratification factor is intended to combine study centers in similar geographic regions. The geographic regions are defined in [Section 3.8](#). The correlation between dose and ACR50 response will be evaluated at a two-sided significance level of $\alpha=0.05$. This evaluation of dose-response will constitute the primary efficacy analysis.

Bimekizumab 160mg with loading dose will be excluded from the dose-response analysis. A table will present the responder rates for placebo, BKZ 16mg, BKZ 160mg, BKZ 320mg, and the correlation statistic of Mantel and Haenszel (ridit score) with the corresponding p-value.

NRI will be used to account for missing data in the primary analysis. That is, subjects with a missing ACR score at Week 12 or who discontinued study treatment prior to the Week 12 visit will be considered non-responders for the primary analysis.

8.1.3 Secondary analyses of the primary efficacy variable

As the secondary analysis for the primary efficacy variable, a logistic regression model will be used to assess the effect of each individual dose versus placebo on ACR50 response. The model will include fixed effects for treatment, geographic region, and prior TNF inhibitor exposure (yes/no). To avoid the problem of the so-called monotone likelihood resulting in infinite large confidence intervals (eg, if one of the cell counts in the 2x2 table is equal to zero), a penalized maximum likelihood approach based on the modified score procedure of Firth (eg, Heinze and Schemper, 2002) will be used in the logistic models. If the logistic regression model is unable to converge, then geographic region may be dropped from the model to facilitate convergence. If the logistic regression model is unable to converge after dropping the geographic region, then prior TNF inhibitor exposure may be dropped as well. Comparisons will be made for each dose versus placebo at a 2-sided significance level of $\alpha=0.05$. For each dose, the odds ratio versus placebo, the 95% CI, and the corresponding p-value will be calculated. In addition, a comparison will be made for the bimekizumab 320mg loading dose followed by bimekizumab 160mg Q4W versus bimekizumab 160mg Q4W using the same logistic model described above.

The pairwise comparisons of bimekizumab versus placebo will be formally evaluated for statistical significance only if the primary dose response efficacy analysis is statistically significant. Once the dose response has been established, pairwise testing of each bimekizumab dose versus placebo will account for multiplicity by using a fixed sequence testing procedure with each bimekizumab dose being tested sequentially from the highest dose to the lowest dose. If the dose-response relationship fails to reach significance at a significance level of $\alpha=0.05$, then the further pairwise comparisons are seen as non-significant.

A table will present the responder rates for placebo, BKZ 16mg, BKZ 160mg w/ LD, BKZ 160mg, BKZ 320mg, and for each dose the odds ratios (differences to placebo), 95% CIs, and corresponding p-values from the logistic regression.

NRI will be used to account for missing data in the primary analysis. That is, subjects with a missing ACR score at Week 12 or who discontinued study treatment prior to the Week 12 visit will be considered non-responders for the primary analysis.

8.1.4 Supportive analyses of the primary efficacy variable

The following supportive analyses are planned:

1. The primary dose response analysis and pairwise comparisons will be repeated for all subjects in the PPS to evaluate the effect of important protocol deviations on the analysis.
2. The primary dose response analysis and pairwise comparisons will be repeated for all subjects in the RS to evaluate the consistency of the FAS with the ITT principle. Subjects with no valid measurement of the primary efficacy variable at Baseline will be included as non-responders. NRI will be used to account for missing data.
3. The change from Baseline in all ACR components (ie, TJC, SJC, PGADA, PhGADA, PtAAP, HAQ-Di, and hs-CRP) will be analyzed using the ANCOVA with treatment group, geographic region, and prior TNF inhibitor exposure as fixed effects and the Baseline values as covariate. MI will be used for missing data (Section 4.2.1).

For the supportive analysis number 1 and 2 two tables will be displayed. One table will present the responder rates for placebo, BKZ 16mg, BKZ 160mg w/ LD, BKZ 160mg, BKZ 320mg, and the correlation statistic of Mantel and Haenszel (ridit score) with the corresponding p-value. The other table will present the responder rates, and for each dose the odds ratios (differences to placebo), 95% CIs, and corresponding p-values from the logistic regression.

For the supportive analysis number 3 tables will present the least-square means and standard error for placebo and bimekizumab dose for the ANCOVA models. For the pairwise comparison between placebo and bimekizumab dose the least-square means, standard error, corresponding p-values, and 95% confidence intervals for the contrasts will be provided.

8.1.5 Sensitivity analyses of the primary efficacy variable

Two sensitivity analyses will be performed for the primary dose response analysis and for the supportive analysis number 3:

1. This analysis evaluates the effectiveness of the treatment (de facto hypothesis) and will be based on the ordered categorical analysis to evaluate dose-response as specified in the primary analysis. In an attempt to prevent missing data during the study, efforts will be made to collect data from subjects that withdraw early from the study. An analysis will be performed in which all available data at Week 12 will be considered. In this case, subjects will be analyzed according to their randomized treatment, even if they discontinued prior to Week 12 and were no longer on the randomized study treatment when the assessment was performed at Week 12. If Week 12 data for the ACR50 response are not collected, the subject will be assumed to be a non-responder. It should be noted that this measures something different from the primary analysis and could be confounded by placebo subjects who withdraw and are subsequently on another active medication at the time of the Week 12 assessment.
2. An additional sensitivity analysis will be based on observed data only for subjects who are still on the initially randomized treatment at Week 12. Subjects with missing data or who have prematurely discontinued study treatment will be excluded from the analysis. The same procedure described for the primary efficacy analysis of dose response will be used.

The following sensitivity analyses will be performed for the supportive analysis for the primary efficacy variable (pairwise comparison analysis of the primary efficacy variable) in order to assess the missing data assumptions:

1. Missing data will be imputed using MI. In MI, the missing value is replaced by a set of plausible values, where each value is a Bayesian draw from the conditional distribution of the missing data given the observed data. Intermittent missing data will be imputed using the MCMC method, followed by monotone regression for monotone missing data to evaluate the effect of the method for handling missing data on the analysis. The ACR components will be imputed individually and then the ACR response will be calculated using the complete datasets. The multiply imputed data sets will be analyzed using a logistic regression model with fixed effects for treatment, geographic region, and prior TNF inhibitor exposure. Finally, the results will be combined into a single inference using Rubin's rule (Carpenter and Kenward, 2013). This procedure assumes a MAR pattern of missingness and corresponds to an estimand of what has been called the difference in outcome improvement if all subjects tolerated or adhered to treatment (Mallinckrodt et al, 2012). More details are available in [Section 4.2.1](#).
2. The logistic regression model will be applied where all available data at Week 12 will be considered, as described in sensitivity analysis (1) for the primary efficacy variable.
3. The logistic regression model will be applied where only observed data for subjects still on the initially randomized treatment at Week 12 will be considered, as described in sensitivity analysis (2) for the primary efficacy variable.

The same tables as used for the primary and secondary efficacy analysis for the primary efficacy variable and for the supportive analysis number 3 with the different imputation analysis will be presented.

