In an attempt to prevent missing data during the study, efforts will be made to collect data from subjects that withdraw early from the study (NRC, 2010). If a subject withdraws from study treatment for any of the above criteria (#4 through #10) prior to Week 12, they will be asked to return for the study assessments 12 weeks after the first dose (ie, Week 12 Visit) and for the SFU Visit (20 weeks after last dose administration). These data will be used in a sensitivity analysis which is described in Section 15.7. If any of these criteria occur after Week 12, subjects will complete an ET Visit and the SFU Visit. All subjects who withdraw from the study due to an AE must be followed until resolution of the event or until the event is considered stable. All subjects who withdraw from the study due to development of a laboratory abnormality specified in Criterion #8 must be closely monitored, with additional monitoring of hepatic markers every week or every 2 weeks until resolution of the event, the event is considered stable, or they have reached the end of the SFU Period for those who at any time have an ALT and/or AST  $>5X$  but  $<8X$  ULN.

Investigators should attempt to obtain information on subjects in the case of withdrawal or discontinuation. For subjects considered as lost to follow-up, the Investigator should make an effort (at least 1 phone call and 1 written message to the subject), and document his/her effort (date and summary of the phone call and copy of the written message in the source documents), to complete the final evaluation. All results of these evaluations and observations, together with a narrative description of the reason(s) for removing the subject, must be recorded in the source documents. The electronic Case Report Form (eCRF) must document the primary reason for withdrawal or discontinuation.

Investigators should contact the Medical Monitor, whenever possible, to discuss the withdrawal of a subject in advance.

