3.5 Mapping of assessments performed at early termination visit

Study assessments at an early termination visit where visit date matches the visit date of a scheduled visit will be summarized at the scheduled visit with the same visit date. Premature study termination visit assessments that do not have a scheduled visit with a matching date will be assigned to the next scheduled site visit following the last visit where assessments were available regardless whether or not there will be an assessment on this visit. The assessment of AbAb is an exception to this rule: AbAb will be mapped to the next visit where antibody levels are measured. For subjects who discontinue study treatment early and return for the Week 12 visits as per the protocol, the assessments collected at that visit are summarized as Week 12 assessments.

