4.2 Handling of dropouts or missing data

4.2.1 Handling of missing data for efficacy analysis

The analysis for the binary primary, secondary, and other efficacy variables will use non-responder imputation (NRI) for handling missing data. In NRI, each subject with missing data or who has discontinued Double-Blind study treatment prior to Week 12 will be counted as a non-responder.

Sensitivity analysis will be performed for the secondary analysis of the primary variable (ACR50 response at Week 12) using MI assuming that missingness is missing at random (MAR). The MI method will be applied as follows:

1. Create a data set, sorted by treatment groups, of subjects with observed values and those needing estimation by multiple imputation. For the imputation step, missing values will be separated into non-monotone missing values (ie, intermittent missing values between completed assessments) and monotone missing values (ie, missing values after the patient dropped out). The procedure will sequentially estimate an imputation model for the ACR components at each post-Baseline visit where ACR components are collected, with geographic region, and prior TNF inhibitor exposure as covariates separated between the treatment groups.

- For the imputation of intermediate missing values, the missing ACR components in each data set will be filled in using the Markov-Chain Monte Carlo (MCMC) method with multiple chains and monotone imputing. A total number of imputations will be 100. The seed used for these imputations will be 2017.

Note: All other multiple imputation procedures described in this SAP will use this same seed as well.

Note: The imputation model based on the MCMC method will only allow continuous variables as predictors. Therefore, prior TNF inhibitor exposure and geographic region will be re-coded as indicator variables (with values of 0 or 1 for each level of the variable).

Note: To avoid that imputed values are outside of the pre-defined range of values for the ACR components (eg, HAQ-DI [0-3]) maximum and minimum values for imputed variable values are specified.

- If the intermediate missing data are imputed, the monotone missing data will be imputed for all patients with monotone regression including geographic region, and prior TNF inhibitor exposure as covariates. The dataset is the output dataset of the partial imputation. Since this dataset already has 100 imputed values at each visit, only one imputation will be performed.

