Note: Maximum and minimum values are specified for imputed variable values to avoid values outside of the pre-defined range of values.

2. The ACR50 response will be calculated using the complete datasets. That is, the values of the ACR components at Week 12 based on the complete datasets will be compared to their corresponding Baseline values to calculate an ACR50 response for each subject (as described in Section 8.1.1). Each complete imputed data set will then be analyzed based on a logistic regression model with factors of treatment group, geographic region, and prior TNF inhibitor exposure as fixed effects.
3. The Week 12 results from the logistic regression analysis of each of the 100 imputed data sets will be combined for overall inference using Rubin's rules, which account for the uncertainty associated with the imputed values (Rubin, 1987).

Some key points to consider relative to the calculation of the odds ratios and corresponding confidence intervals (CIs) are noted below:

As the estimates of the odds ratios from the logistic regression model in step 3 follow a lognormal distribution, a log transformation is needed to normalize these estimates since the procedures for combining results from multiple imputed datasets are based on the assumption that the statistics estimated from each imputed dataset are normally distributed. Therefore, the log of the odds ratio estimates from the logistic regression model are used when combining into a single inference (step 3). Additionally, the standard errors (SE) for the odds ratios are transformed as follows:

$$SE = \frac{\log(UCL) - \log(LCL)}{2Z_{\alpha/2}} \quad (1)$$

where UCL and LCL are the upper and lower confidence limit, respectively, for the CI of the odds ratio from the logistic regression model, and $Z_{\alpha/2}$ is the relevant critical value from the standard normal distribution (1.96 for a 95% CI). The estimates of the log odds ratio for each bimekizumab dose relative to placebo and the corresponding upper and lower confidence limits will be provided. The odds ratio is estimated by exponentiating the estimate of the log odds ratio. The confidence limits of the odds ratio are then estimated as follows:

$$LCL = OR * \exp(-SE * Z_{\alpha/2}) \quad (2)$$

$$UCL = OR * \exp(SE * Z_{\alpha/2}) \quad (3)$$

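### The MI sensitivity analysis is labelled a full-adherence estimand, but nothing sets Week 12 values collected after treatment discontinuation to missing before imputation (minor)

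*SAP*

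**What the plan says.** **The label.** SAP 8.1.5 describes MI of the ACR components under missing at random (MAR), followed by logistic regression and Rubin's rules. It says that this procedure "corresponds to an estimand of what has been called the difference in outcome improvement if all subjects tolerated or adhered to treatment". Protocol 15.7 makes the same claim.

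**The procedure.** SAP 4.2.1 starts from a data set "of subjects with observed values and those needing estimation by multiple imputation". It sorts the gaps into intermittent ones and a second kind, "monotone missing values (ie, missing values after the patient dropped out". ACR50 is then derived from the filled data: "the values of the ACR components at Week 12 based on the complete datasets will be compared to their corresponding Baseline values". None of these steps uses treatment status.

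**The data that reach Week 12.** Under Protocol 6.3, if subjects are withdrawn from study treatment before Week 12 under criteria 4 to 10, "they will be asked to return for the study assessments 12 weeks after the first dose". The protocol adds: "These data will be used in a sensitivity analysis which is described in Section 15.7". For subjects who return, SAP 3.5 says that "the assessments collected at that visit are summarized as Week 12 assessments". The same section assigns an early termination visit with no matching date to the next scheduled visit, so a post-discontinuation assessment can also reach Week 12 by that route.

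**The concern.** A full-adherence estimand asks what would have happened had everyone stayed on treatment. Values measured after treatment has stopped do not answer that question, and an analysis aimed at it would normally discard and impute them. Here a collected Week 12 value is not missing, so a programmer following SAP 4.2.1 would keep it.

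Subjects who stop and return would then contribute their actual off-treatment outcome, while subjects who stop and do not return would contribute an imputed outcome. The kept values also feed the arm-specific imputation models, so they influence the imputed values as well.

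What is at stake is interpretation. The SAP runs these analyses to test the missing-data assumptions, and a reader will take the MI result as the answer to the question it is labelled with.

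**Working it through.** **1. How the Week 12 analyses treat discontinuation**

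- NRI (SAP 4.2.1, 8.1.2): a non-responder is a subject with missing data or one who discontinued before Week 12. The two conditions are named separately.
- Observed, on-treatment analysis (SAP 8.1.5): excludes subjects with missing data and subjects who stopped early. Again both are named.
- All-available-data analysis (SAP 8.1.5): keeps off-treatment values by design and warns of confounding by other active medication.
- MI (SAP 4.2.1, 8.1.5): names missing data only, and carries no such warning.

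The omission is therefore specific to MI.

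**2. The plan's own figure**

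The plan gives no figure for this analysis. Its stated power of >99% concerns the primary trend test. With 40 per arm and two-sided 0.05, a linear-trend calculation gives 0.9992 or more under every score, arm-count and TNF-adjustment variant tried. That test uses NRI and does not depend on the MI.

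**3. Illustrative size**

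Inputs from the documents (Protocol 15.9, SAP 2.4): ACR50 of 58.5% (320mg), 42.2% (160mg) and 8% (placebo); a 25% reduction in up to 30% of subjects for prior TNF inhibitor use. Reading the reduction as relative, the factor is 1 - 0.30 x 0.25 = 0.925.

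- 320mg: 0.585 x 0.925 = 0.541
- 160mg: 0.422 x 0.925 = 0.390

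Assumed, because the documents give no value: 5-15% discontinue, half are retrieved, and off-treatment ACR50 is 8-20%. The share of an arm with a retrieved off-treatment value is f = 0.05 x 0.5 = 0.025 to 0.15 x 0.5 = 0.075, or 1 to 3 subjects out of 40.

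Shift in the arm's rate = f x (on-treatment rate - off-treatment rate):

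| f | 160mg, off-treatment 0.20 | 320mg, off-treatment 0.08 |
|---|---|---|
| 0.025 | 0.025 x 0.190 = 0.5 points | 0.025 x 0.461 = 1.2 points |
| 0.075 | 0.075 x 0.190 = 1.4 points | 0.075 x 0.461 = 3.5 points |

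For scale, the standard error of one arm's rate is sqrt(0.541 x 0.459 / 40) = 7.9 points.

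For 320mg against placebo at 8%, with off-treatment response also at 8%, the difference of 0.461 (odds ratio 13.6) becomes 0.450 (12.9) at f = 0.025 and 0.427 (11.8) at f = 0.075. If retrieved placebo subjects instead respond at 30% on other therapy (a further assumption), f = 0.075 in each arm gives 0.410 (9.6). These scenarios all move toward the null, but the documents do not fix the direction.

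**4. Check by simulation**

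A one-arm regression-MI simulation (target about 0.54, off-treatment rate 0.08, half retrieved) compared the two handlings:

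| Discontinue | Full-adherence rate | Values kept | Values set to missing |
|---|---|---|---|
| 5% | 0.537 | 0.525 | 0.538 |
| 15% | 0.543 | 0.503 | 0.542 |

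Setting the values to missing recovers the target. Keeping them lowers the rate by 1.2 and 4.0 points, against 1.2 and 3.5 from the formula. A somewhat larger shift is expected, because the formula ignores the effect of kept values on the imputations. With 7.5% retrieved and 7.5% not, that adds about 0.075 x (0.075 / 0.925) x 0.461 = 0.3 points.

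**The case against.** The strongest reply is that the sponsor meant to exclude these values.

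- SAP 8.1.5 applies the all-available-data analysis to supportive analysis 3, which already uses the same MI method (SAP 4.2.1, 8.1.4). If that MI kept retrieved values, the extra analysis would add little. It is informative only if the MI leaves them out.
- Protocol 6.3 assigns the retrieved data to a sensitivity analysis in the singular, and Protocol 15.7 describes one built around them.
- SAP 4.2.1 describes monotone missing values as those after drop-out.
- SAP 3.5 governs how visits are summarised, and NRI overrides it without citing it.

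This is fair evidence of intent. A reader might infer that the SAP states that MI uses retrieved values. It does not; the point rests on a missing rule read together with SAP 3.5. But MI is itself a Protocol 15.7 sensitivity analysis, and no sentence tells the programmer to discard a collected Week 12 value. The need for a written rule stands on either reading.

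The reply on size is also largely right. The discontinuation and retrieval rates are assumed. Return is requested only under criteria 4 to 10. The half-life is about 28 days, and double-blind doses fall at Baseline, Week 4 and Week 8 (SAP 2.3). A subject who stops after the Week 8 dose has had every double-blind dose, and one last dosed at Week 4 is about two half-lives out at Week 12. A placebo-level response for such subjects is therefore pessimistic.

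**Conclusion.** Wrong as written, and minor. Followed literally, SAP 3.5 and 4.2.1 do not deliver the estimand stated in SAP 8.1.5. They give a mixture of treatment-policy and adherence outcomes.

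Under the stated assumptions the active-arm rate falls by roughly 0.5 to 3.5 points, plus a few tenths at the upper end through the imputation model. Residual drug exposure probably makes it less. Even the upper end is under half of one arm's standard error.

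Two stronger readings are not supported:

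- A reader might put the upper end at 0.075 x (0.585 - 0.08) = 3.8 points. That uses the 320mg rate before the TNF adjustment that the plan itself applies.
- A reader might infer that the trial's conclusions, or the whole set of sensitivity analyses, are compromised. The primary trend test, its power and the gatekept pairwise tests use NRI. The all-available-data and on-treatment analyses are fully specified for ACR50 and unaffected. The all-available-data analysis also overlaps with MI only in part, because it counts uncollected outcomes as non-response where MI imputes them.

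**What to change.** Add to SAP 4.2.1 and 8.1.5 that, for this analysis, ACR component values collected after discontinuation of double-blind study treatment before Week 12 are set to missing before imputation. Use the NRI definition of discontinuation, and cover early termination values mapped to a scheduled visit. If the sponsor prefers to keep the values, remove the full-adherence label and describe the estimand as a mixture.

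State also:

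- whether the same rule applies to the MI in supportive analysis 3, where it determines what the all-available-data analysis adds;
- which handling the Week 12 interim used, since SAP 4.3.1 includes the sensitivity analyses in that interim and SAP 4.3.1.1 shows that it has been run.

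The cost is a sentence or two in the SAP and one data step, plus a rerun of the MI output if the interim kept the values. Sample size and the primary analysis do not change.
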